Post treatment follow up is for safety collection and is up to 150 days post core phase or extension phase discontinuation (see [Figure 3-1](#)). Survival data will be collected until end of study inclusive of the extension and post treatment follow up duration.

Treatment options and dosing information are provided in [Section 6.1](#). The planned duration of a cycle is 28 days.

Participants who become eligible for hematopoietic stem cell transplant (HSCT) at any time during the course of the study will be discontinued from investigational study treatment (MBG453 (sabatolimab)).

All participants must be followed for adverse events (AEs) after the last dose of MBG453 (sabatolimab) as indicated in [Section 10.1](#). All women of child-bearing potential must be followed for pregnancy safety evaluations as per [Table 8-1](#) and after last dose of MBG453 (sabatolimab) as indicated in [Section 10.1.4](#).

At the end of the study, every effort will be made, in alignment with local regulations, to continue provision of MBG453 (sabatolimab) outside this study through an alternative setting to participants who are receiving treatment with MBG453 (sabatolimab) and in the opinion of the investigator are still deriving clinical benefit. Options for continued treatment with MBG453 (sabatolimab) may include access to commercially available drug, or managed access program, or a roll-over study.

[figure not shown]
There are four separate periods of this study:

1. Screening period (signing of written informed consent through Day of enrollment);
2. Core phase for up to 12 months
3. Extension phase for efficacy and/or survival status (up to 12 months after core phase)
4. post treatment safety follow-up monitoring for adverse events (AEs) for 30 days following the last dose of azacitidine or decitabine or INQOVI (oral decitabine), or 150 days following the last dose of MBG453 (sabatolimab), whichever is later.

[figure not shown]
Approximately 39 patients who are evaluable for primary endpoints will be assessed.

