Clinical Development

MBG453/ Sabatolimab

CMBG453B1US01 / NCT04878432

Single-arm, open label, phase II study of MBG453 (sabatolimab) added to FDA approved Hypomethylating agents of investigator's choice (IV/SC/Oral) for patients with intermediate, high or very high risk myelodysplastic syndrome (MDS) as per IPSS-R criteria (US multi-center)

(STIMULUS MDS-US)

Statistical Analysis Plan (SAP)

Document type: SAP Documentation

Document status: Final - Addendum 02

Release date: 07-FEB-2025

Number of pages: 47

Property of Novartis
For business use only

May not be used, divulged, published or otherwise disclosed
without the consent of Novartis.

Document History – Changes compared to previous final version of SAP.

| Date | Time point | Reason for update | Outcome for update | Section and title impacted (Current) |
|------------|------------------------------------|--|---|--|
| 07-09-2023 | Before Interim analysis or DBL | As protocol was amended due to the halt in recruitment for the STIMULUS MDS-US study on 30-Sep-2022. | shortening the timeline of the study as well as various administrative changes. Amendment 01 (Based on protocol incl. amendment 02 from 08-Feb-2023) | Section 1.1 Study design Section 1.2 Study objectives and endpoints Section 2.2.1 Subgroup of interest Section 2.5.4 Supportive analyses Section 2.7.1.2 Progression Free Survival Section 2.7.1.3 Overall Survival, Section 2.7.1.8 Improvement in RBC/platelets transfusion independence Section 2.8.4.1 ECG and cardiac imaging data Section 3 Sample size calculation |
| 05-11-2024 | Before Final analysis or Final DBL | Objectives and endpoints Survival follow-up missed | Overall survival endpoints were updated from 12 months to 24 months survival follow-up added to summarize. | [REDACTED] [REDACTED] [REDACTED] [REDACTED] Section 1.2 study objectives & endpoints Section 2.31 |

| Date | Time point | Reason for update | Outcome for update | Section and title impacted (Current) |
|------------|------------|--|--|---|

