A total of 39 subjects were enrolled in this study. Subjects were recruited from sites within the United States. No pre-treatment stratification is planned. The investigator or designee must ensure that only subjects who meet all the inclusion and none of the exclusion criteria are enrolled in the study.

There are 4 types of periods/phases: Screening phase, core phase, extension phase and post treatment safety follow-up

Screening phase: A signing of written informed consent obtained through day 1 of enrollment (from up to 28 days of period prior to core phase start date).

[figure not shown]
Core phase: A 12 months of treatment period is a **core phase**

Extension phase: Extension phase for efficacy and/or survival status (up to 24 months of last subject enrolling) or in addition to core phase (12 months), an additional 12 months of treatment period is **extension phase**.

Post treatment safety follow up: Post treatment safety follow-up monitoring for adverse events (AEs) for 30 days following the last dose of azacitidine or decitabine or INQOVI (oral decitabine), or 150 days following the last dose of MBG453 (sabatolimab), whichever is later.

Figure 1-1 Study design

Study design

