2.2 Analysis sets

The analysis sets to be used as defined below. The FAS will be used for efficacy analysis. The Safety Set will be used for all the safety analysis.

Full Analysis Set

The FAS comprises all enrolled subjects to whom took any component of the study treatment.

Safety Set

The Safety Set includes all subjects who received at least one dose of any component of the study treatment (MBG453 + HMA).

[REDACTED]

[REDACTED]

[REDACTED]

1. [REDACTED]

2. [REDACTED]

[REDACTED]

3. [REDACTED]

[REDACTED]

[REDACTED]

[REDACTED]

Subject Classification

Subjects may be excluded from the analysis populations defined above based on the protocol deviations entered in the database and/or on specific subject classification rules defined in Table 2-1.

Table 2-1 Subject classification based on protocol deviations and non-protocol deviations criteria

| Analysis | Protocol deviations leading to exclusion | Non Protocol deviations leading to exclusion |
|----------|--|--|
|----------|--|--|

| | | |
|------------|-----------------------------|---|
| FAS | No written informed consent | None |
| Safety Set | No written informed consent | No dose of any component of study treatment |
| [REDACTED] | [REDACTED] | [REDACTED] |
| [REDACTED] | [REDACTED] | [REDACTED] |

Withdrawal of Informed Consent

Any data collected in the clinical database after a subject withdraws informed consent from all further participation in the study will not be included in the analyses. The date on which a subject withdraws consent is recorded in the eCRF.

Additional data for which there is a separate informed consent, e.g. biological sample etc., collected in the clinical database without having obtained that consent or after withdrawal of consent will not be included in the analyses.

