2.10 Interim analysis

An interim analysis was performed after all subjects who have completed 6 months follow-up from enrollment (cycle 1 day 1) or discontinued earlier for publication purpose.

Final Analysis will be performed when all subjects complete the core and extension phase and safety follow-up or discontinued early. A final CSR will be written.

3 Sample size calculation

This is an open label, non-randomized, single-arm combination study to assess safety and efficacy of MBG453 (sabatolimab) given with HMAs of investigator's choice (IV/ SC/ Oral). The primary objective of the study is to assess safety profile of this combination drug by 12 months.

Given the above expected incidence rates of AEs with the combination (Table 1-3 of protocol), a sample size of 81 evaluable subjects is estimated based on a two sided 95% confidence interval for an incidence rate of an AE using the large sample normal approximation that will extend 0.10 from the observed incidence rate of an AE (precision or margin of error of 10%) for an expected incidence rate of 30%.

Thus, with the estimated sample size of 90 subjects there is at least 90% probability to detect an AE with a true incidence rate of 2.5%. Considering drop-out rate of 10%, approximately 90 subjects will be enrolled for safety and efficacy assessment of this study.

Novartis has decided to permanently halt recruitment based on a re-evaluation of the development strategy for sabatolimab. Subjects who are currently on study treatment or in follow-up will be continue per the protocol. At the time of this amendment, 39 subjects have been enrolled into the study.

4 Change to protocol specified analyses

- [REDACTED]
- [REDACTED]
- No supportive/subgroup/sensitivity analysis performed due to MBG program closing/due to fewer sample size. Additionally it is mentioned in protocol that subgroup analysis may be performed. Hence it is agreed to not have these analysis.

5 Appendix

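### SAP section 3 still presents the pre-halt sample-size claims (81 evaluable, about 90 to be enrolled, 90% detection of a 2.5% AE) and gives no precision or detection figure for the 39 patients enrolled

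*SAP*

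**What the plan says.** SAP section 3 (Sample size calculation) bases the size of the study on a "two sided 95% confidence interval for an incidence rate of an AE using the large sample normal approximation". In the present tense it gives 81 evaluable subjects for a margin of 10 percentage points at an expected AE rate of 30%. It allows for 10% drop-out and states that "approximately 90 subjects will be enrolled for safety and efficacy assessment of this study". It adds a detection claim: "with the estimated sample size of 90 subjects there is at least 90% probability to detect an AE with a true incidence rate of 2.5" per cent.

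The last paragraph of the same section reports the permanent recruitment halt and ends: "At the time of this amendment, 39 subjects have been enrolled into the study". SAP section 1.1 gives the number as final: "A total of 39 subjects were enrolled in this study".

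The SAP's document history lists "Section 3 Sample size calculation" among the parts affected by the update dated 07-09-2023, whose stated reason is the halt. Two further updates followed (05-11-2024 and 07-02-2025, the latter after database lock), and the sentences are still there.

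The protocol reads differently. Section 12.7 puts the 81-patient calculation in the past tense and contains neither the 90-subject sentence nor the detection sentence. Section 3 says: "Approximately 39 patients who are evaluable for primary endpoints will be assessed".

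**The concern.** The section describes as still to come an enrolment that had already been stopped at fewer than half that number. It also attributes to the study a precision and a detection probability that it does not have. It is silent on what the achieved sample size provides.

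This matters because the primary objective is the safety profile and both documents rule out formal hypothesis testing. In a descriptive safety study, the width of the interval around an AE rate and the chance of seeing an uncommon AE at all are what tell a reader how much weight the results bear. Section 3 is the only place in the SAP where these are stated. A clinical study report that took over the section would repeat figures the trial cannot meet, and would not say how weakly 39 patients rule out an AE that was never observed.

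**Working it through.** **Inputs.** From SAP section 3: two-sided 95% interval by normal approximation, expected rate 30%, half-width 0.10, drop-out 10%, detection at 90 subjects of a true rate of 2.5%, and 39 enrolled (also SAP section 1.1). From protocol Table 1-3, which section 3 cites: all-grade AE rates from 30% to 45%. Assumption: all 39 are in the Safety Set, which takes in anyone who received at least one dose of any component (SAP section 2.2). The documents do not give its actual size.

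**The plan's own figures**
- Evaluable subjects: 1.96² × 0.30 × 0.70 / 0.10² = 80.7, rounded up to 81. Reproduces.
- Enrolment: 81 / 0.90 = 90. Reproduces.
- Detection, 1 − (1 − p)^n: 1 − 0.975^90 = 0.8976, or 89.8%. This is just under the stated minimum of 90%; a full 90% needs ln 0.10 / ln 0.975 = 90.95, so 91 subjects. The difference is one of rounding.

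**The same quantities at 39, with n = 35 as an assumed lower case**

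| Quantity | Formula | Stated in SAP | n = 39 | n = 35 |
|---|---|---|---|---|
| 95% half-width at 30% | 1.96 × √(0.21/n) | 10 points (81 evaluable) | 14.4 points | 15.2 points |
| Probability of at least one case, true rate 2.5% | 1 − 0.975^n | at least 90% (90 subjects) | 62.7% | 58.8% |
| Lowest true rate detected with 90% probability | 1 − 0.10^(1/n) | 2.5% (90 subjects) | 5.7% | 6.4% |
| Exact two-sided 95% upper bound when no case is seen | 1 − 0.025^(1/n) | not given | 9.0% | 10.0% |

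At 45%, the highest all-grade rate in Table 1-3, the half-width at 39 is 1.96 × √(0.2475/39) = 0.156, or 15.6 points.

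The normal approximation does not drive the result. For 12 of 39 (30.8%) the exact 95% interval is 17.0% to 47.6%.

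The chance of missing a 2.5% AE altogether rises from 100 − 89.8 = 10.2% at 90 subjects to 100 − 62.7 = 37.3% at 39.

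**The case against.** The strongest defence is that a sample-size section records how the study was designed, and the design arithmetic is sound. The detection sentence is tied expressly to 90 subjects and claims nothing about 39. The halt and the 39 are in the same section, so nothing is hidden. No test or planned analysis depends on 81 or 90, and readers of the report will have the real denominators. Protocol section 12.7 also gives no figure for 39, so asking for one in the SAP looks like a double standard. The document history may mean only that the halt paragraph was added. Finally, figures added after database lock cannot inform planning.

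Much of this stands. It is uncorrected wording rather than concealment or a calculation error, no result changes, and the 35-patient case is only an assumption.

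It does not remove the defect. The statement that about 90 will be enrolled contradicts SAP section 1.1 outright. Protocol section 12.7 differs because it is in the past tense and promises neither an enrolment nor a detection probability. The SAP keeps both, and it governs the final report. Section 4 of the SAP cites the smaller sample as a reason for dropping supportive, subgroup and sensitivity analyses, so the sponsor treats the shortfall as consequential without stating its effect on the primary objective. The post-lock timing is a reason to label the change, not to leave the old claim standing.

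**Conclusion.** The concern holds and should be fixed. SAP section 3 states an enrolment and a safety-detection capability that the study does not deliver, and it gives no operating characteristics for the number enrolled. The loss is material: precision at a 30% rate falls from 10 to 14.4 points, detection of a 2.5% AE falls from about 90% to 62.7%, and the rate detectable with 90% probability rises from about 2.5% to about 5.7%. These figures assume that all 39 enrolled patients are in the Safety Set; a smaller set makes each of them worse. The effect is on how the primary safety results are read, not on any estimate. The gap between 89.8% and at least 90% is a minor rounding point.

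**What to change.** In SAP section 3 and the matching text of the study report:
- Label the 81/90 calculation as the original plan and put it in the past tense.
- Delete the statement that about 90 subjects are to be enrolled.
- Change at least 90% to approximately 90% (89.8%).
- Add one line for the achieved size. For n = 39: 95% half-width of 14.4 points at 30% and 15.6 at 45%; 62.7% probability of seeing a 2.5% AE; 90% detection for true rates of about 5.7% or more; upper bound of 9.0% when no case is seen. If the Safety Set is smaller than 39, use its actual size.

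Protocol section 12.7 needs no change. Because the current SAP addendum is dated after database lock, mark the edit as a post-lock clarification. The cost is a few lines of text and less favourable stated figures. It needs no protocol amendment, no further patients and no change to any planned analysis.

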5.1 Date of first administration of investigational drug /HMA

The date of first administration of investigational drug /HMA is defined as the first date when a non-zero dose of investigational drug /HMA is administered and recorded on the study treatment eCRF page.

5.2 Date of last administration of of investigational drug /HMA

The date of last administration of the investigational drug /HMA is defined as the last date when a non-zero dose of the respective investigational drug /HMA is administered and recorded on the study treatment eCRF page. So both, first and last date of investigational drug /HMA, are derived separately for each drug which is part of the study treatment.

5.3 Date of first administration of study treatment (combination)

The date of first administration of study treatment (or start date of study treatment) is defined as the first date when a non-zero dose of any component of the study treatment (MBG453 (sabatolimab) in combination with HMAs (IV/SC/Oral)) is administered.

5.4 Date of last administration of study treatment (combination)

The date of last administration of study treatment (or end date of study treatment) is defined as the last date when the last non-zero dose of any last component of the study treatment (MBG453 (sabatolimab) in combination with HMAs (IV/SC/Oral)) is administered.

5.5 Date of last exposure to HMA and investigational drug and date of last exposure to study treatment (combination)

One planned cycle length is 28 days. HMA drugs are planned to be administered every cycle between Day 1 and Day 9 with different schedules. MGB453 is administered every 4 weeks, on Day 8 out of a 28 days cycle, unless there was a toxicity leading to a dosing interval increase.

As treatment is given in cycles, the date of last administration of study treatment is not considered the date of last exposure but instead the planned end date of the last cycle in which the last non-zero dose was given.

The **date of last exposure to MBG453** is therefore calculated as:

- Minimum (last date of administration of investigational drug + 27 days, date of death, last contact date in case subject is lost to follow-up), as MBG453 injections is given Q4W (in case of change to Q8W, the cycle would end after 55 days)

The **date of last exposure to HMA** drugs is calculated as:

The date of last exposure to azacitidine

- Minimum (last date of administration of azacitidine + 20 days, date of death, last contact date in case subject is lost to follow-up) as azacitidine is given daily every cycle during

7 days at the beginning of each cycle (between Day 1 to Day 9) (total cycle length 28 days).

The date of last exposure to decitabine

- Minimum (last date of administration of decitabine + 22 days, date of death, last contact date in case subject is lost to follow-up) as decitabine is given daily every cycle during 5 days at the beginning of each cycle (between Day 1 to Day 5) (total cycle length 28 days).

The **date of last exposure to study treatment (combination)** is calculated as the minimum date between the end date of the last cycle initiated with any component of the study treatment, the date of death and the last contact date in case subject is lost to follow-up. The end date of the last cycle initiated is the planned end date (Day 28) of the last cycle initiated where MBG453 and/or HMA were last administered or the date of the last administration of a non-zero dose of any last component of the study treatment (MBG453, HMA), whichever is the latest. The duration of exposure to study treatment (combination) will be calculated as follow: date of last exposure to study treatment (combination) - date of first administration of study treatment (combination) + 1.

The planned end date of a cycle (Day 28) will be applicable even if this date goes beyond the data cutoff date (it should not be truncated to the date of data cutoff).

5.6 Duration of study treatment (combination) used to calculate the dose intensity and the relative dose intensity

For the calculation of the dose intensity and relative dose intensity, the cycle-based exposure to study treatment (combination) will be derived from the date of first administration of study treatment (combination) to the actual or planned end date of the last cycle initiated (whichever is the latest) irrespective of date of death, last contact date for withdraw consent and cut-off date.

The start date of the first cycle initiated is the first date when a non-zero dose of HMA.

The end date of the last cycle initiated is the planned end date (Day 28) of the last cycle initiated where MBG453 and/or HMA were last administered or the date of the last administration of a non-zero dose of any component of the combination, whichever is the latest.

The duration of study treatment in days used to derive the dose intensity and the relative dose intensity will be calculated as follow: end date of the last cycle initiated – date of first administration of study treatment (combination) + 1.

The planned end date of a cycle (Day 28) will be applicable even if this date goes beyond the data cutoff date, the date of death or the date of last contact date for withdraw consent (it should not be truncated to the date of data cutoff, the date of death or the date of last contact date).

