**Table 6-2 Study drugs**

Study Drug (Name and strength)	Dose Administration	Pharmaceutical Dosage Form	Route of Administration	Obtained by
Decitabine 50mg single vial**	20mg/m2 D1-D5	Lyophilized powder	Intravenous use	Site
Decitabine Oral (INQOVI)	100mg cedazuridine / 35mg decitabine QD D1 to D5	Tablet	Oral	Site
Azacitidine 100 mg single vial**	75mg/m2 D1-D7 or D1 to D5 + D8 & D9	Lyophilized powder	Intravenous or subcutaneous use	Site

\*\*Other locally available dose strengths are acceptable

Azacitidine and decitabine regimens used in this protocol were selected because they are the most studied regimens and recommended by international treatment guidelines (National Comprehensive Cancer Network (NCCN), European Society for Medical Oncology (ESMO), [Steensma 2018](#)). Azacitidine and decitabine are considered as a Standard of Care in the population enrolled in this study and it should be administered according to standard local clinical practice.

Decitabine should be administered according to local standard clinical practice. A standard dose of decitabine (20 mg/m^2) will be given intravenously every day for five consecutive days on Days 1-5 out of a 28 days cycle (see local decitabine US package insert) or 100mg/35mg QD D1 to D5 out of a 28 days cycle if using oral formulation. The food intake requirement for oral formulation should be consistent with approved oral decitabine label, no food should be consumed 2 hours before and 2 hours after each dose of oral decitabine. MBG453 (sabatolimab) infusions will be administered on Day 8 out of a 28 days cycle (For IV and SC HMs, sabatolimab (MBG453) can be administered on a day between days 5-8 as per investigator decision) ([Table 8-1](#)).

Azacitidine should be administered according to local standard clinical practice. A standard dose of azacitidine (75 mg/m^2) will be given subcutaneously or intravenously every day for seven consecutive days on Days 1-7 out of a 28 days cycle (see local azacitidine US package insert). In keeping with standard clinical practice, the alternative schedule of 75 mg/m^2 for five consecutive days on Days 1-5, followed by a two-day break, then two consecutive days on Days 8-9 will also be permitted (alternative schedule). MBG453 (sabatolimab) infusions will be

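### The HMA last-exposure formulas in SAP 5.5 miss the intended Day 28 cycle end on every planned schedule: by one day after a complete last cycle, and by up to seven days if dosing stopped early

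*SAP*

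**What the plan says.** SAP 5.5 starts from the cycle: "One planned cycle length is 28 days". It then says that the date of last administration is not the date of last exposure, which is "instead the planned end date of the last cycle in which the last non-zero dose was given". The formulas follow.

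- Azacitidine: "Minimum (last date of administration of azacitidine + 20 days, date of death, last contact date in case subject is lost to follow-up"), justified by seven dosing days between Day 1 and Day 9 of a 28-day cycle.
- Decitabine: "Minimum (last date of administration of decitabine + 22 days, date of death, last contact date in case subject is lost to follow-up"), on the ground that "decitabine is given daily every cycle during 5 days at the beginning of each cycle (between Day 1 to Day 5"). No separate formula is given for the oral form, which Protocol Table 6-2 also schedules on Days 1 to 5.
- MBG453: last dose plus 27 days, explained by the four-weekly interval, with 55 days mentioned for a change to eight-weekly dosing.

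For the combination, the same section works from the cycle directly: "The end date of the last cycle initiated is the planned end date (Day 28) of the last cycle initiated", or the last dose if that is later. Protocol Table 6-2 permits two azacitidine schedules: "75mg/m2 D1-D7 or D1 to D5 + D8 & D9". SAP 2.4.1 reports duration of exposure for the combination and for each drug, with the HMAs shown separately and pooled.

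**The concern.** The text of SAP 5.5 and its HMA formulas define different dates. There are two separate faults.

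First, the offsets themselves do not lead from the last planned dose to Day 28. Since azacitidine may end on Day 7 or Day 9, no single offset can serve both schedules.

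Second, the offset is added to the last dose actually given. Under the stated rule, any dose in a cycle carries exposure to the end of that cycle, however many doses followed. Under the formula, each dose dropped from the end of a consecutive-day course moves the end date earlier. Protocol 6.5 allows HMA treatment to be modified within a cycle or interrupted for adverse events, so shortened last cycles are foreseeable.

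At stake is a reported safety-context summary: the HMA durations would not match their own definition, nor the combination duration printed beside them.

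**Working it through.** **Inputs.** Cycle length 28 days, target Day 28, decitabine offset +22 and azacitidine offset +20 (all SAP 5.5). Last planned dose: Day 5 for decitabine; Day 7 or Day 9 for azacitidine (Protocol Table 6-2).

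**Counting convention.** A dose on Day k plus n days falls on Day k + n. Day 1 + 27 = Day 28, which reproduces the combination rule's cycle end and agrees with the +27 used for a 28-day MBG453 interval.

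**Complete last cycle.** Day reached = last dose day + offset. Offset needed = 28 − last dose day.

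| Schedule | Last planned dose | SAP offset | Day reached | Gap from Day 28 | Offset needed |
|---|---|---|---|---|---|
| Decitabine, Days 1–5 | 5 | +22 | 27 | −1 | +23 |
| Azacitidine, Days 1–7 | 7 | +20 | 27 | −1 | +21 |
| Azacitidine, Days 1–5 and 8–9 | 9 | +20 | 29 | +1 | +19 |

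The SAP's own offsets can be reproduced as 27 − 5 = 22 and 27 − 7 = 20, whereas 28 − 5 = 23 and 28 − 7 = 21 would reach Day 28 on the consecutive-day schedules. This suggests an off-by-one slip, but that origin is inferred; the SAP does not state it.

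**Last cycle stopped early.**

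- Decitabine, last dose on Day 4, 3, 2 or 1: Day 26, 25, 24 or 23, which is 2 to 5 days short.
- Azacitidine Days 1–7, last dose on Day 6, 5, 4, 3, 2 or 1: Day 26, 25, 24, 23, 22 or 21, which is 2 to 7 days short.
- Azacitidine Days 1–5 and 8–9: missing only Day 9 gives 8 + 20 = Day 28, which is exact; missing Days 8 and 9 gives 5 + 20 = Day 25, which is 3 days short.

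**Relative size.** One cycle: 1/28 = 3.6% and 7/28 = 25%. Thirteen cycles (13 × 28 = 364 days): 1/364 = 0.27% and 7/364 = 1.9%. One day is 1/30.4375 = 0.03 months on the SAP's month length (2.1.1.5).

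**Which outputs use these dates.**

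- Duration of exposure for each HMA and for HMAs pooled (SAP 2.4.1): yes.
- Combination exposure (SAP 5.5): no; it uses Day 28 of the last cycle initiated.
- Dose intensity and relative dose intensity (SAP 2.4.1 and 5.6): no; they run to the end of the last cycle initiated.
- AE tables (SAP 2.8 and 2.8.1): no; the on-treatment window runs to 30 days after the last dose, and the tables give numbers and percentages of subjects.

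**MBG453, for comparison.** Day 8 + 27 = Day 35 and Day 5 + 27 = Day 32, both later than the combination's Day 28 for the same last cycle.

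**The case against.** The strongest reply is that almost nothing depends on these dates. They enter no endpoint, sample size or error rate. One day over a 13-cycle course is 0.27%. The seven-day figure needs a last azacitidine cycle with a Day 1 dose only. Where death or a lost-to-follow-up contact date comes first, the minimum applies and the offset has no effect. The latest SAP update is marked as made after database lock, so the practical gain is small. All of this stands, and it fixes the severity at minor. It does not make the formulas agree with the rule they implement.

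Four stronger readings are tempting and are not supported.

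- A reader might infer that AE rates are distorted. The plan has no exposure-adjusted AE rate, and the AE window is set from the last dose.
- A reader might infer that the offsets always shorten exposure. On the Days 1–5 and 8–9 azacitidine schedule a complete cycle overshoots by one day, and missing only Day 9 removes the error. Protocol section 8 also allows administration up to seven days late for reasons other than toxicity, and a late last dose moves the date later.
- A reader might infer that most participants are off by about a day and some by a week. The documents give neither the mix of schedules nor the number of shortened last cycles.
- A reader might count the MBG453 formula as the same mistake. Its +27 days has a stated dosing-interval reason and equals one four-week interval counting the dosing day. It fits awkwardly with the cycle-end sentence above it, but that is a matter of wording.

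**Conclusion.** The point holds as a minor error of derivation. After a complete last cycle, the HMA last-exposure date is one day early for decitabine and for seven-day azacitidine, and one day late for the Days 1–5 and 8–9 schedule. If dosing stops early on a consecutive-day schedule, it is up to 5 days early for decitabine and up to 7 for azacitidine. The effect is confined to the descriptive HMA durations of exposure and matters mainly for participants with few cycles.

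This rests on reading the HMA formulas as implementing the cycle-end rule. The placement supports that: the formulas follow the rule in the same section and cite the 28-day cycle as their reason. The figures also assume that doses fall on their planned cycle days and that neither death nor a lost-to-follow-up contact date intervenes.

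**What to change.** For each HMA (IV decitabine, oral decitabine, azacitidine), define last exposure as the start date of the last cycle in which a non-zero dose of that HMA was given plus 27 days, or the last dose date if later. Keep the caps at death and at last contact for participants lost to follow-up. When neither cap nor a later dose applies, this gives Day 28 on both azacitidine schedules and after a shortened cycle, and it matches the combination rule. Replacing the offsets with +23 and +21 would not be enough: the Day 9 schedule needs +19, and no fixed offset works when dosing stops early.

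As a wording note only, say that the MBG453 +27 days is a dosing-interval convention that can run past the combination's Day 28 end.

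The cost is a few lines of SAP text, one derivation in the exposure dataset and a rerun of the HMA duration summaries. No new data are needed, since the combination rule already requires the end date of the last cycle. Because the SAP was last updated after database lock, record the change as a post-lock correction. No dosing or clinical rule is touched.
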